4.1 Study Duration

The entire study will last for 2 years.

Phase 1 will be conducted in the first year. Participants will participate in one interview or focus group that will last approximately 1.5 hours.

Phase 2 will be conducted in the second year of the study. Participants will participate in a 6-month intervention.

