5.3 Eligibility Criteria

Phase 1 eligibility criteria for adults with T2D

In order to be eligible for inclusion in the study, an individual must meet all of the following criteria:

- Established patient of one of the partner CHCs;
- Age ≥ 18 years;
- Diagnosed with T2D ≥ 6 months;
- Able to read in English or Spanish.

Any individual who meets any of the following criteria will be excluded from participation in this study:

Cognitive impairment (≥ 3 errors on the Six Item Screener for cognitive impairment in clinical research [SIS]) (Callahan et al. 2002) as they will have difficulty in completing the study requirements

Gestational diabetes

Diagnosis of type 1 diabetes

Phase 1 eligibility criteria for health care providers

In order to be eligible for inclusion in the study, an individual must meet all of the following criteria:

Health care provider or community health worker at one of our partner CHC

Provides care/services for adults with T2D

Any individual who meets any of the following criteria will be excluded from participation in this study:

None

Vulnerable/special populations that will be included are: economically or educationally disadvantaged populations and elderly populations (who do not demonstrate cognitive impairment). These groups have health disparities with respect to patient portal use and are important to include in the research to be able to address their needs and improve health equity and health outcomes.

Phase 2: Inclusion criteria are: established patient of one of the partner CHCs; age 18 years or older; diagnosed with T2D >6 months; most recent A1C >7.5%; no current use of patient portal, no intention of moving/changing clinic within 6 months; and able to read in English or Spanish. Exclusion criteria include: cognitive impairment and gestational diabetes.

Participants who participated in Phase 1 will be eligible to participate in Phase 2.

Vulnerable/special populations that will be included are: economically or educationally disadvantaged populations and elderly populations (who do not demonstrate cognitive impairment). These groups have health disparities with respect to patient portal use and are important to include in the research to be able to address their needs and improve health equity and health outcomes.

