Training will also teach CHWs and nurses how to provide autonomy support to participants. Research shows that autonomy support can be learned and practiced.⁴⁸⁻⁵¹ Through scripts, role-play, and illustrative case examples, they will be trained to use specific techniques such as acknowledging the participant perspective, identifying participant goals, emphasizing participant responsibility, and providing encouragement. The co-PIs will observe role plays and complete treatment fidelity checklists; CHWs and nurses will be allowed to deliver the intervention to participants only after the PIs judge that their skill level is sufficient. Drs. [name] and [name] have extensive experience training CHWs and nurses in delivery of behavioral interventions. After the formal training, the PIs, the study nurse and CHW will meet approximately weekly during the first four weeks of intervention delivery and bi-weekly thereafter or as indicated by the PIs. Clinics will be compensated for the salary of the nurse and CHW for training, delivering the intervention, and completing study tasks.

Follow-up data will be collected at 3 and 6 months. At each data collection session, an appointment for the next data collection session will be scheduled. Participants will be sent a text message, email message, phone call, or calendar reminder (based on preference) for data collection appointments (3, 2, and 1 day prior). To maximize retention, we will explain all study procedures in the informed consent process, provide escalating incentives for study assessments, and collect data on alternate contact persons. Our research team has ample experience with longitudinal research demonstrating successful retention with hard to reach populations including Latinx adults with T2D. Study participants will receive compensation for data collection (Baseline \$40.00, 3-month \$40.00, 6-month \$60.00)

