7.1 Sample Size Considerations

Phase 1: Not applicable

Phase 2: Since this is a pilot study to provide preliminary data for a future large study, we conducted a power analysis to show an effect size on A1C using a feasible sample size of 30 participants. We chose the more conservative approach to power on A1C vs. portal logins as we anticipate a smaller effect size on A1C. In our recent study with low-income Latinx adults, we obtained a standard deviation of 1.2 and a sample correlation of 0.57 in repeatedly measured A1C over 6 months. The estimated standard deviation of changed A1C will be 0.72 and the sample size of 30 will produce a standard error of 0.13. Therefore, the proposed sample size of 30 could estimate a change of A1C over time with a margin of $\pm 0.27\%$ A1C for 95% confidence interval.

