7.2 Planned Analyses

Phase 1 analysis:

The sample of participants in the interviews/focus groups will be described using frequency distributions and appropriate summary statistics (SAS version 9.4). Content analysis will be used to analyze qualitative data from each type of stakeholder along with field notes and interviewer observations (Hsieh, 2005) Rigor for this process includes: (a) transcribing taped interviews; (b) checking transcripts against tapes for accuracy; (c) developing coding categories by two members of the research team; (d) assigning codes of text with appropriate checks; (e) reviewing coded data to identify themes across participants; and (f) a team approach to data analysis. At research team meetings we will assess researcher bias, coding saturation, and interpretative congruence. Results will be used to finalize the intervention protocol for implementation in Phase 2

Phase 2 Analysis: Data will be collected in the form of questionnaires online on the secure REDCap system. A1C data, electronic medical record data and patient portal data will be entered into REDCap or Excel and merged into one database. All data that are downloaded from REDCap or Excel will be onto a Yale server, which has several secure firewall systems. Descriptive analyses will be performed to assess demographic and clinical characteristics of the sample. Feasibility data will be summarized. Distributions of outcome variables will be examined for central tendency and dispersion. We will estimate the Cohen's D effect size of MAP on A1C and will examine the intervention effect over 6 months using generalized linear mixed model (GLMM) with random intercept, which will incorporate the correlation within repeatedly measured A1C. The slope of time will represent the average change of A1C over 6 months. The GLMM will include all participants with data at baseline and at least one of post-intervention value and will handle missing data using maximum likelihood approach. To confirm findings with missing data, we will rerun the GLMM with multiple imputations which will be produced by assuming multivariate normal distribution of repeatedly measured A1C. Number of logins and the repeatedly measured secondary outcomes will be analyzed with the same approach using the GLMM. Residuals will be assessed for normality assumption and

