7.7 Handling of Missing Data

Phase 1: Not applicable

Phase 2: To confirm findings with missing data, we will rerun the GLMM with multiple imputations which will be produced by assuming multivariate normal distribution of repeatedly measured A1C. Number of logins and the repeatedly measured secondary outcomes will be analyzed with the same approach using the GLMM.

8 Data/Specimen Handling and Record Keeping

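### The A1C mixed model leaves out participants seen only at baseline, which would bias the estimated change modestly if early loss depends on baseline A1C; keeping them in costs almost nothing

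*Combined protocol and SAP*

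**What the plan says.** Section 7.2 (Phase 2 Analysis) analyses A1C at baseline, 3 and 6 months "using generalized linear mixed model (GLMM) with random intercept, which will incorporate the correlation within repeatedly measured A1C". The slope of time is read as the average change over 6 months. The analysis set is defined by one sentence: "The GLMM will include all participants with data at baseline and at least one of post-intervention value". Within that set the model "will handle missing data using maximum likelihood approach".

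The only further step for missing data appears in 7.2 and again in 7.7: "To confirm findings with missing data, we will rerun the GLMM with multiple imputations which will be produced by assuming multivariate normal distribution". Neither section says whether the imputation covers everyone enrolled or only those already admitted to the model. Section 7.2 applies the same approach to the number of logins and the repeated secondary outcomes.

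Section 7.1 gives an A1C SD of 1.2, a correlation of 0.57 over 6 months, an SD of change ("The estimated standard deviation of changed A1C will be 0.72"), a standard error of 0.13 and a margin of ±0.27 for 30 participants. No attrition rate is stated. Section 6.1 plans active retention: the team will "provide escalating incentives for study assessments, and collect data on alternate contact persons".

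**The concern.** Loss that depends only on an observed baseline A1C is missing at random. A likelihood model handles such loss if the baselines of those who leave stay in the data and the covariance is right. The inclusion rule takes those baselines out, so the model is fitted to a group selected on baseline. Because A1C regresses toward its mean, the average change in that group differs from the average change among all enrolled.

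What is at stake is the accuracy of an estimate. Phase 2 exists to supply an A1C effect size for a later, larger study, and that figure should refer to everyone who enrolled. The imputation rerun would expose the difference only if it includes the baseline-only participants. Otherwise it would repeat the same figure and appear to confirm it.

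**Working it through.** **1. The plan's own precision figure (7.1).** 0.72/√30 = 0.131, and 0.131 × t(0.975, 29) = 0.131 × 2.045 = 0.27. The standard error and margin follow from 0.72. But 0.72 does not follow from SD 1.2 and r = 0.57: 1.2 × √(2 × 0.43) = 1.113, which gives SE 0.203 and a margin of ±0.42. An SD of change of 0.72 needs r = 1 − 0.72²/(2 × 1.2²) = 1 − 0.5184/2.88 = 0.82. That mismatch is a separate matter. Here both correlations are carried through.

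**2. Bias formula.** With equal SDs, the expected change given baseline Y0 is δ − (1−r)(Y0 − μ). Let p be the share seen only at baseline and D the mean baseline of those lost minus that of those retained. The retained mean baseline is then μ − pD, so the retained group's expected change is δ + (1−r)pD. The bias is **(1−r) × p × D**.

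**3. Illustration.** Assumed, not in the documents: true change −0.50, p = 0.20, normal baseline, log-odds of loss +0.5 or +1.0 per A1C point. From 7.1: SD 1.2. Solving for the gap gives D = 0.68 or 1.18 A1C points.

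| r | log-odds | (1−r) × p × D | estimate under the planned rule |
|---|---|---|---|
| 0.57 | 0.5 | 0.43 × 0.20 × 0.68 = 0.058 | −0.44 |
| 0.57 | 1.0 | 0.43 × 0.20 × 1.18 = 0.101 | −0.40 |
| 0.82 | 0.5 | 0.18 × 0.20 × 0.68 = 0.024 | −0.48 |
| 0.82 | 1.0 | 0.18 × 0.20 × 1.18 = 0.042 | −0.46 |

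Large simulated data sets, fitted by maximum likelihood with a random intercept, agree (−0.442, −0.395, −0.477, −0.458). Keeping all baselines in the same model gives −0.501, −0.497, −0.502 and −0.501.

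**4. Variations under the planned rule.**
- Random loss: −0.500 at both correlations.
- Low-baseline participants lost (log-odds −0.5/−1.0): −0.557/−0.601 at r = 0.57 and −0.525/−0.542 at r = 0.82.
- 10% loss (log-odds +0.5/+1.0): −0.470/−0.447 at r = 0.57 and −0.488/−0.477 at r = 0.82.

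**5. At n = 30.** With r = 0.57, 20% baseline-only loss, a baseline gap of 0.86 SD and 5% random loss at month 6 (1,500 runs), the bias is +0.101 under the planned rule and +0.008 with all baselines. Coverage of the 95% interval is 92.7% and 93.8%. The empirical SD of the estimate is 0.231 in both.

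**6. Imputation.** Using the assumptions of step 3, multivariate-normal imputation over all enrolled followed by the random-intercept model returns −0.498 to −0.503. Imputing only within the model's set reproduces the planned-rule result (−0.440/−0.399 at r = 0.57).

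**7. Unequal spread (assumed).** With SD 1.0 at baseline and 1.2 later, the planned rule gives −0.471/−0.444 at r = 0.57 and −0.497/−0.497 at r = 0.82. Adding baselines under the random intercept gives −0.513/−0.522 and −0.516/−0.532. That is nearer the truth in the first case and slightly further from it in the second.

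**8. Linear time with an unstructured covariance.** With complete data at three equally spaced visits, the random-intercept slope equals month 6 minus baseline, whatever happens at month 3. An unstructured fit of linear time adjusts this by k times the month-3 departure from the line. Assume changes of −0.40 at month 3 and −0.50 at month 6, and correlations of 0.65 (0–3), 0.80 (3–6) and 0.57 (0–6). The departure is −0.40 − (−0.25) = −0.15. Then k = (0.80 − 0.65)/[1 + (2 + 2 × 0.57)/4 − (0.65 + 0.80)] = 0.15/0.335 = 0.448. The slope is −0.50 + 0.448 × 0.15 = −0.43 with nobody lost, where the planned model gives −0.50.

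**The case against.** The strongest reply is that the effect may never arise. No dropout rate or mechanism is given, retention is actively planned, and log-odds of 1.0 mean that those lost start about 1 SD higher than those who stay. At n = 30, sampling error (about 0.23) exceeds every bias shown, and Phase 2 tests no stated hypothesis. This stands, and it sets the point's weight. It does not justify discarding data already collected that the planned model can use.

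Four stronger readings are tempting, and the documents do not support them:

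- **The covariance must change along with the inclusion rule.** Section 7.1 gives one SD and one correlation. On those, restoring the baselines to the planned model is enough. Selection at entry ("most recent A1C >7.5%; no current use of patient portal") makes unequal spread possible, but every unequal SD used above is assumed. Linear time with an unstructured covariance can itself bias the 6-month change (step 8).
- **The imputation omits baseline-only participants.** The text does not say. For that sensitivity analysis the fault is an unstated set, not a proven omission. The primary fit is restricted in either case.
- **A month-6 value is required, because the intervention lasts 6 months.** Only one visit falls at month 6, so asking for at least one later value would then be an empty phrase. Month 3 is most naturally included.
- **The reported Cohen's d is biased by the same amount.** Section 7.2 does not say that d is taken from the mixed model, so this cannot be computed.

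**Conclusion.** The rule does exclude baseline-only participants from the primary A1C model, and the conditional bias is real. In the 20% illustration it is 0.06 to 0.10 A1C points at r = 0.57 (12% to 20% of the assumed 0.50) and 0.02 to 0.04 at r = 0.82. It depends on the assumed share lost, the assumed link to baseline, and equal SDs across visits. It is nil if loss is unrelated to baseline, and its direction depends on who leaves. All of these values lie inside the stated ±0.27. The documents do not show that the A1C result will be biased, and nothing here would overturn a finding. This is a minor, worthwhile improvement. It does not address loss that depends on A1C values never observed.

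**What to change.** (a) In 7.2, let every enrolled participant with a baseline A1C enter the maximum-likelihood model, whether or not a later value exists. Apply the same rule to the other repeated outcomes analysed by this approach.

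(b) In 7.2 and 7.7, state that the multivariate-normal imputation covers all enrolled participants.

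Keep the random-intercept model as the main analysis, and do not require linear time with an unstructured covariance. If a check on the covariance is wanted, fit visit as a category with an unstructured covariance and report the month-6 minus baseline contrast as a sensitivity analysis.

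The cost is a few lines of wording and code, with no new data. There is one downside: if A1C spread is smaller at baseline than later, adding baselines to the random-intercept model can slightly overstate the reduction (about −0.51 to −0.53 against −0.50 for SD 1.0 then 1.2). The optional sensitivity analysis would reveal this.

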Glycosylated Hemoglobin (A1C)	A1C now point of care with fingerstick of blood
Secondary:	
Engagement with care	Clinic appointments Referrals ER visits Hospitalizations Use of community resources
T2D clinical management	EMR data: dates of service, A1C, blood pressure, lipid profile, height, weight, BMI
T2D self-management	Self-rated health (1 item); Medication adherence, blood glucose monitoring, healthy eating, physical activity (24 items)
Psychosocial outcomes	Diabetes self-efficacy (8 items) Autonomy support (health care climate) (7 items) Diabetes distress (20 items)
Technology acceptance/use	Digital health literacy (3 items) Technology acceptance (8 items) Technology use (6 items) Technology confidence (4 items) Tablet use (3 items)

	Barriers/Facilitators (13 items)
Satisfaction	Satisfaction with program (4 items) Satisfaction with health care provider (3 items)
Use of community resources	1 items

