6.6 Locations/Facilities

Phase 1: Interviews/focus groups, if able to be scheduled in-person, will be conducted at the CHC in a private room. Our clinic locations are Fair Haven Community Health Center in New Haven and Norwalk Community Health Center in Norwalk, CT. Interviews/focus groups may also be conducted by phone or ZOOM. We will provide participants access to ZOOM and instructions how to use it, if they are not familiar with this platform.

Phase 2: Data collection will be collected from participants in-person at the clinic or private location preferred by participants or via telehealth for study questionnaires. A1C data will be collected at the clinic or private location preferred by participants. Electronic health record and patient portal data will be collected by trained clinic personnel at each clinical site.

7 Statistical Design

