8.5 Access to Source

Phase 1: Not applicable.

Phase 2: Source data consists of data collected from the electronic medical record and from the patient portal. Select personnel at each clinic will collect this data, record or export data to a study record form, de-identify the data, and securely transfer it to the PIs.

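### The imputation meant to confirm the A1C result uses only the repeated A1C series and gives no role to the dated EMR A1C already in the study database.

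*Combined protocol and SAP*

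**What the plan says.** The primary A1C is a study measurement, listed in Table 1 (6.1.1) as "A1C now point of care with fingerstick of blood", taken at baseline, 3 and 6 months. The main analysis in 7.2 is a GLMM with a random intercept, with missing values handled by maximum likelihood. Its analysis set is defined as follows: "The GLMM will include all participants with data at baseline and at least one of post-intervention value". As confirmation, the model is to be refitted with "multiple imputations which will be produced by assuming multivariate normal distribution of repeatedly measured A1C". Section 7.7 repeats this ("we will rerun the GLMM with multiple imputations which will be produced by assuming multivariate normal distribution") and adds no other imputation input.

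Table 1 also lists a second source of A1C, as a secondary outcome: "EMR data: dates of service, A1C, blood pressure, lipid profile, height, weight, BMI". Section 6.6 says who obtains it: "Electronic health record and patient portal data will be collected by trained clinic personnel at each clinical site". Section 8.5 says how: "Select personnel at each clinic will collect this data, record or export data to a study record form". Section 7.2 then brings the sources together: "A1C data, electronic medical record data and patient portal data will be entered into REDCap or Excel and merged into one database". Neither 7.2 nor 7.7 gives the EMR A1C a role in handling missing fingerstick values.

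**The concern.** A sensitivity analysis for missing data is useful if it changes an assumption or adds information. The planned rerun does neither to any real extent. Likelihood and standard multiple imputation both assume missingness at random given the observed values, both assume normality, and here both condition on the same A1C series. Agreement between them would say little about whether missing values have distorted the result. They can differ a little, because the GLMM as described imposes a linear slope and a single random intercept, and because the rerun may or may not include people with no post-baseline value.

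Suppose people whose A1C is rising are the ones who miss the 6-month fingerstick. Predicting their value from earlier fingersticks then overstates the fall, in both analyses. A routine A1C dated near the visit carries information about the missing value that earlier fingersticks do not. Phase 2 exists to estimate an effect size for a later, larger study, so a check that could reveal an overstated fall is worth having.

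**Working it through.** **The plan's own precision figure, for scale.** Section 7.1 gives SD 1.2, correlation 0.57, SD of change 0.72, SE 0.13 and a margin of ±0.27. The last two follow from 0.72: 0.72/√30 = 0.131, and 2.045 × 0.131 = 0.27. But 0.72 does not follow from 1.2 and 0.57: 1.2 × √(2 × 0.43) = 1.11, which gives SE 1.11/√30 = 0.20 and margin 2.045 × 0.203 = 0.42. That is a separate matter. Both margins are used below only as yardsticks.

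**How much each source says about a missing 6-month value.** Take r = 0.57 from 7.1 and assume it holds between every pair of visits.
- Baseline only: R² = r² = 0.32; residual SD = 1.2 × √0.675 = 0.99.
- Baseline and 3 months: R² = 2r²/(1 + r) = 0.650/1.57 = 0.41; residual SD = 1.2 × √0.586 = 0.92.
- Add a same-window EMR A1C with assumed correlation a to the fingerstick. With v the residual variance before EMR (0.586 or 0.675, in SD units), the new residual variance is 1/[1/v + 1/(1/a² − 1)]. For a = 0.90 and v = 0.586: 1/(1.706 + 4.263) = 0.168, so R² = 0.83.
- Over a = 0.80 to 0.95, R² is 0.71 to 0.91 with the 3-month value present and 0.69 to 0.91 without it.

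The fingerstick series therefore explains 32-41% of the variance of a missing 6-month value. With an EMR value on file this becomes about 69-91%.

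**Effect on the mean change.** The documents give no dropout rate, EMR coverage or EMR-fingerstick correlation, so everything in this step is assumed except SD 1.2 and r 0.57. The set-up is a true fall of 0.40 and about 20% missing at 6 months, with the odds of being missing 2.5 times higher per SD of A1C rise. Half of those missing also lack the 3-month value. The estimates are multivariate-normal maximum-likelihood means from large simulated samples, with and without one EMR A1C near 6 months. Coverage means the share of people with a missing fingerstick who have an EMR value.

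| Coverage among those missing | Overstatement of the fall without EMR | With EMR (correlation 0.8 to 0.95) |
|---|---|---|
| 70% | 0.13-0.14 | about 0.055-0.09 |
| 30% | 0.13-0.14 | about 0.09-0.11 |
| 10% | 0.13-0.14 | about 0.12-0.13 |

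A second simulation used n = 30, complete 3-month data, and missingness driven by the 6-month level (logit slope 0.7 per SD). At nominal 20% missing, the overstatement was about 0.105 without EMR. With EMR it was about 0.09 at 30% coverage, 0.06-0.08 at 50% and 0.03-0.065 at 80%. At nominal 10% and 30% missing, the figures without EMR were about 0.055 and 0.15.

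**Precision.** If values are missing completely at random there is no bias either way. At n = 30 the SE falls by about 2-6%, for example from 0.213 to 0.204.

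**Head count.** Twenty per cent of 30 is 6 people. EMR coverage of 70%, 30% or 10% supplies a value for about 4, 2 or fewer than 1 of them.

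**The case against.** Several points on the other side stand.

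- *The main estimate does not move.* A reader might infer that the planned primary estimate is biased and that the EMR value would correct it. The documents do not support this. The mechanism of missingness is unknown, the primary analysis is the likelihood GLMM, and the change proposed here touches only the confirmatory rerun. The simulations also use an unstructured normal model and keep people with only a baseline value, whom the planned GLMM leaves out, so their figures are not the bias of the planned estimator.
- *EMR coverage may be poor exactly where it is needed.* A reader might infer that many missing fingersticks have an EMR value. The abbreviation table describes A1C as measured roughly every three months, which is encouraging. But 7.3 says this population's engagement with clinical care is often inconsistent, 6.6 already allows the fingerstick away from the clinic, and 6.5 lets some participants opt out of data collection. People who still miss the fingerstick may also lack routine results, so the 10-30% rows of the table are realistic.
- *The EMR value is a proxy and is not thrown away.* It comes from routine care, possibly by another assay and on another date, so it is not a direct reading of the missing fingerstick. It is a named secondary outcome, so it would be wrong to say that the plan discards it.
- *The effect is modest for a pilot.* In the middle case (correlation 0.9, 70% coverage) about 0.07 is removed, a third of an SE of about 0.21.
- *The wording is not exclusive.* The phrase repeatedly measured A1C does not expressly rule out EMR values. Sections 7.1 and 7.2 use it for the modelled outcome series, though, so the fingerstick reading is the natural one.

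These points limit the size of the benefit. They do not remove the observation that the rerun adds little as written, or that a better input is already in the database.

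**Conclusion.** The point holds as a cheap improvement to a sensitivity analysis. As written, the imputation shares its data and assumptions with the main model and will largely repeat it, while a dated second A1C source has no role in handling missing values. Nothing in the plan is invalid or contradictory on this account.

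Under the assumed 20% informative missingness, the possible overstatement of 0.13-0.14 is about half the plan's stated ±0.27 margin and about a third of the recomputed ±0.42. EMR data would remove roughly a third to three fifths of it at 70% coverage, less at 30%, and almost none at 10%. If missingness is completely random, the gain is a slightly smaller SE. Which case applies cannot be settled from the documents, because coverage among people with missing fingersticks is not given. The conclusion that the rerun is weak confirmation does not depend on these figures; only the size of the gain does.

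**What to change.** In 7.2 and 7.7, before any outcome data are examined, add wording such as:

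> The imputation model will also include, as auxiliary variables, the EMR A1C dated closest to the 3-month and to the 6-month visit within ±6 weeks, left missing when none exists. EMR values will not replace fingerstick values and will not enter the analysis model. The imputed analysis will include participants who have no post-baseline fingerstick. The report will give the proportion of missing fingersticks with an EMR A1C in the window, and the agreement between EMR and fingerstick A1C where both exist.

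The ±6 weeks is an example. Counted from visits at 13 and 26 weeks it gives windows of 7-19 and 20-32 weeks, which do not overlap. Whatever window is chosen should be fixed in advance, since choosing it after seeing results would be data-driven.

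The cost is a few sentences and a few lines of code. No new type of data is needed, but the EMR extraction must run to the end of the second window. Use at most one EMR value per visit: going from three to five variables raises the means and covariances to be estimated from 9 to 20, which is already a lot for 30 people. If reported coverage turns out low, the report should say that the imputed analysis offers little independent confirmation.
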